3.4.2 Other Restrictions and Precautions

Inhaled or topical steroids, and adrenal replacement steroid doses > 10 mg daily prednisone equivalent, are permitted in the absence of active autoimmune disease.

3.5 Discontinuation of Participants from Treatment with Study Drugs

Participants MUST discontinue investigational product (and non-investigational product at the discretion of the investigator) for any of the following reasons:

- Subject's request to stop study treatment
- Any clinical AE, laboratory abnormality or intercurrent illness which, in the opinion of the investigator, indicates that continued participation in the study is not in the best interest of the subject
- Pregnancy
- Loss of ability to freely provide consent through imprisonment or involuntarily incarceration for treatment of either a psychiatric or physical (eg, infectious disease) illness
- Additional protocol specified reasons for discontinuation (see Section 4.3.5)

All participants who discontinue investigational product should comply with protocol specified follow-up procedures as outlined in Section 5 - Study Assessment and Procedures. The only exception to this requirement is when a subject withdraws consent for all study procedures including post-treatment study follow-up or loses the ability to consent freely (ie, is imprisoned or involuntarily incarcerated for the treatment of either a psychiatric or physical illness). If study treatment is discontinued prior to the subject's completion of the study, the reason for the discontinuation must be documented in the subject's medical records and entered on the appropriate case report form (CRF) page.

3.6 Post Study Drug Follow Up

Post treatment study follow-up is of critical importance and is essential to preserving subject safety and the integrity of the study. Participants who discontinue study treatment must continue to be followed for collection of outcome and/or survival follow-up data as required and in line with Section 5 Study Assessments and Procedures until death or the conclusion of the study.

3.6.1 *Withdrawal of Consent*

Participants who request to discontinue study treatment will remain in the study and must continue to be followed for protocol specified follow-up procedures. The only exception to this is when a subject specifically withdraws consent for any further contact with him/her or persons previously authorized by subject to provide this information. Participants should notify the investigator of the decision to withdraw consent from future follow-up in writing, whenever possible. The withdrawal of consent should be explained in detail in the medical records by the investigator, as to whether the withdrawal is from further treatment with study drug only or also from study procedures and/or post treatment study follow-up and entered on the appropriate CRF page. In the event that vital status (whether the subject is alive or dead) is being measured, publicly available information should be used to determine vital status only as appropriately directed in accordance with local law.

3.6.2 *Lost to Follow-up*

All reasonable efforts must be made to locate participants to determine and report their ongoing status. This includes follow-up with persons authorized by the participant as noted above. Lost to follow-up is defined by the inability to reach the participant after a minimum of three documented phone calls, faxes, or emails as well as lack of response by subject to one registered mail letter. All attempts should be documented in the participant's medical records. If it is determined that the participant has died, the site will use permissible local methods to obtain the date and cause of death. If after all attempts, the participant remains lost to follow-up, then the last known alive date as determined by the investigator should be reported and documented in the subject's medical records.

4. STUDY DRUG

4.1 Investigational Product

An investigational product, also known as investigational medicinal product in some regions, is defined a pharmaceutical form of an active substance or placebo being tested or used as a reference in a clinical study, including products already with a marketing authorization but used or assembled (formulated or packaged) differently than the authorized form, or used for an unauthorized indication, or when used to gain further information about the authorized form. The investigational product should be stored in a secure area according to local regulations. It is the responsibility of the investigator to ensure that investigational product is only dispensed to study participants. The investigational product must be dispensed only from official study sites by authorized personnel according to local regulations.

In this protocol, investigational products are nivolumab and ipilimumab. See Table 4-1.

Table 4.1: Study Drugs for QUAD-01

Product Description/Class and Dosage Form	Potency	IP/Non-IMP	Blinded or Open Label	Packaging/Appearance	Storage Conditions (per Label)
Nivolumab Solution for Injection	100 mg (10 mg/mL)	IP	Open-Label	Clear to opalescent colorless to pale yellow liquid. May contain particles.	2 to 8°C. Protect from light, freezing and shaking.
Ipilimumab Solution for Injection	200 mg (5 mg/mL)	IP	Open-Label	Clear, colorless to pale yellow liquid. May contain particles.	2 to 8°C. Protect from light and freezing.
Encorafenib	50 or 75 mg	Non-IMP	Open-Label		
Binimetonib	45mg	Non-IMP	Open-Label		

4.2 Non-Investigational Product

Other medications used as support or escape medication for preventative, diagnostic, or therapeutic reasons, as components of the standard of care for a given diagnosis, may be considered as non-investigational products. In this protocol encorafenib and binimatinib are non-investigational products.

4.3 Storage and Dispensing

The product storage manager should ensure that the study drug is stored in accordance with the environmental conditions (temperature, light, and humidity) as determined by BMS. If concerns regarding the quality or appearance of the study drug arise, the study drug should not be dispensed and contact BMS immediately.

Investigational product documentation (whether supplied by BMS or not) must be maintained that includes all processes required to ensure drug is accurately administered. This includes documentation of drug storage, administration and, as applicable, storage temperatures, reconstitution, and use of required processes (eg, required diluents, administration sets).

Infusion-related supplies (eg IV bags, in-line filters, 0.9% NaCl solution) will not be supplied by the sponsor and should be purchased locally if permitted by local regulations.

For non-investigational product, if marketed product is utilized, it should be stored in accordance with the package insert, summary of product characteristics (SmPC), or similar.

Please refer to the current version of the encorafenib, binimatinib, nivolumab and ipilimumab IBs and/or pharmacy reference sheets for complete storage, handling, dispensing, and infusion information.

Nivolumab

Nivolumab vials must be stored at a temperature of 2° C to 8° C and should be protected from light, freezing, and shaking. If stored in a glass front refrigerator, vials should be stored in the carton. Recommended safety measures for preparation and handling of nivolumab include laboratory coats and gloves.

For details on prepared drug storage and use time of nivolumab under room temperature/light and refrigeration, please refer to the nivolumab IB section for "Recommended Storage and Use Conditions" and/or pharmacy reference sheets. Care must be taken to assure sterility of the prepared solution as the product does not contain any anti-microbial preservative or bacteriostatic agent. No incompatibilities between nivolumab and polyolefin bags have been observed.

Nivolumab is to be administered as an IV infusion per institution SOC using a volumetric pump with a 0.2/0.22 micron in-line filter at the protocol-specified dose. The drug can be diluted with 0.9% normal saline for delivery, but the total drug concentration of the solution

Phase I/II study of encorafenib and binimatinib with nivolumab and low dose ipilimumab in metastatic *BRAF* mutant melanoma

cannot be below 0.35 mg/mL. It is not to be administered as an IV push or bolus injection. At the end of the infusion, flush the line with a sufficient quantity of normal saline.

Ipilimumab

Ipilimumab injection can be used for IV administration without dilution after transferring to a PVC (polyvinyl chloride), non-PVC/non-DEHP (di-(2-ethylhexyl)phthalate) or glass containers and is stable for 24 h at 2 °C–8°C or room temperature/room light (RT/RL). For ipilimumab storage instructions, refer to ipilimumab IB and/or pharmacy reference sheets. Recommended safety measures for preparation and handling include protective clothing, gloves, and safety cabinets.

Ipilimumab is to be administered as an IV infusion per institution SOC, using a volumetric pump with a 0.2 to 1.2 micron in-line filter at the protocol-specified dose. The drug can be diluted with 0.9% normal saline or 5% Dextrose Injection to concentrations between 1 mg/mL and 4 mg/mL. It is not to be administered as an IV push or bolus injection. Care must be taken to assure sterility of the prepared solutions, since the drug product does not contain any antimicrobial preservatives or bacteriostatic agents.

When both study drugs are to be administered on the same day, separate infusion bags and filters must be used for each infusion. Nivolumab is to be administered first. The nivolumab infusion must be promptly followed by a saline flush to clear the line of nivolumab before starting the ipilimumab infusion.

Encorafenib

Encorafenib 450 (quadruple) or 300 (triple) mg will be administered PO QD continuously. Patients should take encorafenib daily in the morning at approximately the same time every day.

Binimatinib

Binimatinib 45 mg will be administered PO BID continuously. Patients will be instructed to take binimatinib 12 ± 2 h apart in the morning and in the evening at approximately the same times every day.

Encorafenib and binimatinib should be taken together, if applicable, and without regard to food. Patients will be instructed to swallow the capsules/tablets whole with a large glass of water and not to chew or crush them.

4.4 Method of Assigning Subject Identification

QUAD-01 study is an open-label study. Patients must not start protocol treatment prior to registration in the Clinical Trials Management Application (CTMA). Participants can be enrolled after eligibility criteria are met. Registration will require the following information: 1) protocol name and number, 2) date treatment begins, 3) subject name, 4) date of birth, 5) primary study physician, 6) confirmation of eligibility, 7) and verification that the informed consent was signed.

Phase I/II study of encorafenib and binimatinib with nivolumab and low dose ipilimumab in metastatic *BRAF* mutant melanoma

4.5 Selection and Timing of Dose for Each Subject

Dosing and schedules for QUAD-01 are outlined in Table 4.5A and 4.5B. The investigational products nivolumab at 3mg/kg and ipilimumab at 1mg/kg will be given every 3 weeks for the first 4 treatments, then switched to single agent nivolumab at 480mg flat dose for up to one year. Encorafenib with or without binimatinib will be dosed as shown in Table 4.5A.

Table 4.5A: Dosing Schedule for Phase I

	Day 1 Week 1	Day 1 Week 2	Day 1 Week 3	Day 1 Week 4	Day 1 Week 5	Day 1 Week 6	Day 1 Week 7
Cohort 1: Triple therapy (encorafenib + nivolumab + ipilimumab)	300 mg encorafenib PO daily						
	3mg/kg Nivolumab			3mg/kg Nivolumab			3mg/kg Nivolumab
	1mg/kg Ipilimumab			1 mg/kg Ipilimumab			1 mg/kg Ipilimumab
Cohort 2: Quadruple therapy (encorafenib + binimetinib + nivolumab + ipilimumab)	450 mg encorafenib PO daily						
	45 mg binimetinib PO BID						
	3mg/kg Nivolumab			3mg/kg Nivolumab			3mg/kg Nivolumab
	1mg/kg Ipilimumab			1 mg/kg Ipilimumab			1 mg/kg Ipilimumab

*Investigational products nivolumab and ipilimumab will be administered every 3 weeks for the first four doses, then single agent nivolumab will be administered every 4 weeks at flat dose of 480mg for up to one year.

Phase I/II study of encorafenib and binimetinib with nivolumab and low dose ipilimumab in metastatic *BRAF* mutant melanoma

Table 4.5B: Dosing Schedule for Phase II

	Day 1 Week - 2	Day 1 Week - 1	Day 1 Week 1	Day 1 Week 2	Day 1 Week 3	Day 1 Week 4	Day 1 Week 5
Group 1: Brain metastases	RP2R	RP2R	RP2R	RP2R	RP2R	RP2R	RP2R
Group 2: Elevated LDH OR Bulky Visceral Disease SLD > 44 mm	RP2R	RP2R	RP2R	RP2R	RP2R	RP2R	RP2R

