Phase I/II study of encorafenib with and without binimetinib with nivolumab and low dose ipilimumab in metastatic *BRAF* mutant melanoma

Rationale:

After meeting with Principal Investigators at participating sites to discuss enrollment, decision was made to allow one cycle of immunotherapy prior to enrollment based on data from SECOMBIT and DREAM-Seq trials which have established sequential therapy with upfront immunotherapy as a standard of care. While dual checkpoint inhibition with CTLA4 and PD1 is the most likely combination, we will also allow single agent immunotherapy as well. This will allow patients who were started on checkpoint inhibition in the community to participate and increase accrual.

Major Changes:

- Expanded inclusion criteria throughout protocol.

Amendment 4

Changes to exclusion criteria to allow patients with history of thromboembolic events that are on stable dosing of anti-coagulants per investigator discretion.

Rationale:

The PI in conjunction with the treating investigators has identified that protocol exclusion criteria #12 is at odds with a common presentation of relevant patients for this protocol and is potentially adverse to the best treatment of such patients. The treatment population for the protocol are those with high-risk and/or large tumor burden, where concurrent venous thromboembolism is a common occurrence.

Major changes:

- Updates to exclusion criteria

SYNOPSIS

Clinical Protocol HCC 20-190

Protocol Title:

A Multi-Center Phase I/II Open Label Study to Evaluate Safety and Efficacy in Participants with Metastatic *BRAF*-mutant Melanoma Treated with Encorafenib with and without Binimetinib in Combination with Nivolumab and Low-dose Ipilimumab. (QUAD 01: Quadruple Therapy in Melanoma).

Investigational Product(s), Dose and Mode of Administration, Duration of Treatment with Investigational Product(s):

Encorafenib 450 mg orally (PO) daily (QD) plus binimetinib 45 mg PO twice daily (BID) together with nivolumab administered intravenously (IV) at 3mg/kg and ipilimumab administered IV at 1 mg/kg every 3 weeks for 4 doses, followed by nivolumab administered IV at 480mg every 4 weeks until progression or discontinuation due to toxicity.

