Concurrently, a triple therapy arm will be explored with encorafenib 300 mg PO QD together with ipilimumab administered IV at 1mg/kg and nivolumab 3mg/kg IV every 3 weeks for 4 doses, followed by nivolumab administered at 480mg every 4 weeks until progression or discontinuation due to toxicity.

Tolerability of the two arms will be compared, and a recommended phase II regimen (RP2R) will be determined.

After determination of treatment regimen, expansion cohorts will further explore the preliminary efficacy and further describe the toxicity profile of the triplet or quadruplet regimen in high-risk cohorts including symptomatic brain metastases or liver metastases with elevated lactate dehydrogenase (LDH) or bulky systemic disease burden.

Study Phase: 1/2

Research Hypothesis: Treatment with encorafenib + nivolumab + ipilimumab (triple therapy) and/or treatment with encorafenib + binimetinib + nivolumab + ipilimumab (quadruple therapy) will demonstrate adequate safety and tolerability in unresectable or metastatic *BRAF*-mutant melanoma high-risk patients.

Objectives

Primary Objective

- To nominate a recommended phase II regimen (RP2R) of triple or quadruple therapy with encorafenib (+/- binimetinib) + nivolumab and + ipilimumab in *BRAF*-mutated, metastatic melanoma.

Secondary Objectives

Phase I/II study of encorafenib with and without binimetinib with nivolumab and low dose ipilimumab in metastatic *BRAF* mutant melanoma

- To estimate the RECIST response rate of triple or quadruple therapy in high-risk populations of *BRAF*-mutated, metastatic melanoma.
- To estimate the CNS clinical benefit rate (CBR, defined as complete response [CR] + partial response [PR] + stable disease [SD] > 6 months) per RANO-MB criteria of triple or quadruple therapy in *BRAF*-mutated, metastatic melanoma to the CNS
- To describe the toxicity, using Criteria for Adverse Events version 5 (CTCAEv5), of triple or quadruple therapy in *BRAF*-mutated, metastatic melanoma
- To summarize the progression-free survival of triple or quadruple therapy in high-risk populations of *BRAF*-mutated, metastatic melanoma

Exploratory Objective

- To evaluate the association between treatment response and baseline tumor mutational burden, changes in the tumor microenvironment (interferon [*IFN*]-associated gene expression), T cell clonality, and other biospecimens before and after therapy.

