3.2 Post Study Access to Drug

At the end of the study, BMS will not continue to provide BMS supplied study drug to participants/investigators unless BMS chooses to extend the study. The investigator should ensure that the subject receives appropriate care to treat the condition under study. Participants who continue to respond at the end of on study treatment may be prescribed study medication through commercial supply.

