5. STUDY DESIGN

5.1 Overall Design

Table 5.2.1 details assessments for Phase 1 Cohort 1, and Table 5.2.2 for Phase 1 Cohort 2. Every effort must be made to follow the schedule of assessments within the windows outlined in the protocol.

- For the first 6 weeks, all assessments have a \pm 3 day window unless otherwise indicated.
- After the first 6 weeks, all assessments have a \pm 7 day window, unless otherwise indicated. Additional assessment may be performed as clinically indicated.

If study drug is being held due to toxicity, then the scheduled visits and assessments should still be performed per protocol (except dose administration), unless otherwise specified.

Table 5.2.2: Phase I Cohort 1															
Trial Period:		Screen Phase	Treatment										End of Treatment	Post-Treatment	
Treatment Cycle/Title:		Screen	D1 W1	D1 W2	D1 W3	D1 W4	D1 W5	D1 W6	D1 W7	D1 W8	D1 W9	D1W 14 (+)	Discon	Safety Follow-up	Follow Up Visits
Scheduling Window (Days):	28 days	± 3	± 3	± 3	± 3	± 3	± 3	± 3	± 3	± 3	± 3	At time of Discon	100 days post discon	Every 12 weeks post discon	
Informed Consent	X														
Inclusion/Exclusion Criteria	X														
Demographics and Medical History	X														
Prior and Concomitant Medication Review	X	X			X			X			X	X			
Trial Treatment Administration ^a		X			X			X			X	X			
Review Adverse Events	X	X			X			X			X	X			
Nursing Call Check-Up			X	X		X	X		X	X		X			
Physical Examination	X	X			X			X			X	X	X	X	X
Vital Signs	X	X			X			X			X	X	X	X	X
ECOG Performance Status	X	X			X			X			X	X	X	X	X
Pregnancy Test	X														
EKG	X														
CBC with Differential	X	X	X	X	X			X			X	X	X	X	X
Comprehensive Serum Chemistry Panel	X	X	X	X	X			X			X	X	X	X	X
HCV, HIV, HepB	X														
TSH (T3, FT4 if TSH abnormal)	X	X	X	X	X			X			X	X	X	X	X
Research blood collection ^b	X				X								X		
Archival tumor collection	X														
Fresh tumor biopsy ^c	X				X ^c										
Imaging ^d	X														

- a. Encorafenib and binimetonib are given continuously. Nivolumab and ipilimumab are given for four doses every 3 weeks then nivolumab is given monthly for up to one year.
- b. Blood will be drawn at baseline, week 4, week 12 (or with first restaging imaging) and at progression/end of treatment

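### Nivolumab maintenance has no time limit in the Synopsis but is capped at one year, with no stated start point, in section 4.5 and the schedule footnotes

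*Combined protocol and SAP*

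**What the plan says.** Two rules for the length of nivolumab maintenance stand in the current text.

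**No time limit.** The Synopsis item on product, dose and treatment duration describes the quadruple regimen as induction "followed by nivolumab administered IV at 480mg every 4 weeks until progression or discontinuation due to toxicity". It describes the triple regimen in the same way: "followed by nivolumab administered at 480mg every 4 weeks until progression or discontinuation due to toxicity".

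**A one-year limit.** The text of section 4.5 has patients "then switched to single agent nivolumab at 480mg flat dose for up to one year". The footnote to Table 4.5A says "then single agent nivolumab will be administered every 4 weeks at flat dose of 480mg for up to one year". In section 5.1, footnote a of the Cohort 1 schedule and of the Cohort 2 schedule says "Nivolumab and ipilimumab are given for four doses every 3 weeks then nivolumab is given monthly for up to one year".

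Table 4.5B, for Phase II, gives only the selected regimen (RP2R) and no duration, so Phase II inherits whichever rule is read into it.

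**The concern.** Nivolumab is an investigational product here, and the trial is multi-site with no control arm. A site working from the Synopsis would continue nivolumab in a progression-free patient after a year. A site working from section 4.5 or the schedules would stop it. Even sites that apply the cap could stop at different times, because the start of the year is not given.

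The secondary objective is to summarize PFS for the regimen. If the length of one component varies by site, PFS beyond about one year describes a mixture of treatment durations. Cumulative exposure and late toxicity are mixed in the same way. Analysis cannot undo this afterwards, because the duration given would be tied to the site.

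**Working it through.** No sample size, error rate or confidence bound in section 8 depends on the maintenance duration, so there is no planned figure to reproduce. The check is a comparison of text, followed by two calculations for scale.

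**Step 1. Does any passage reconcile the rules?**
- Section 3.5 lists reasons for stopping study drug. Neither progression nor completing a year is among them. It adds "Additional protocol specified reasons for discontinuation (see Section 4.3.5"), but there is no section 4.3.5 in the table of contents or the body.
- Section 3.2 says "Participants who continue to respond at the end of on study treatment may be prescribed study medication through commercial supply". This foresees an end to on-study treatment but gives no time.
- Section 4.10 covers toxicity and dosing delays, not a planned end of treatment.
- No clause gives the Synopsis or the body precedence.

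**Step 2. What does one year mean in doses?** Induction every 3 weeks from week 1 falls on weeks 1, 4, 7 and 10. The section 5.1 schedules show the next treatment at week 14, and maintenance is every 4 weeks.
- Year counted from first dose: weeks 14, 18, ..., 50, so (50 - 14)/4 + 1 = 10 doses.
- Year counted from start of maintenance: weeks 14, 18, ..., 62, so (62 - 14)/4 + 1 = 13 doses.
- Synopsis rule: no limit.

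Starting at week 13 gives the same counts, with last doses at weeks 49 and 61.

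**Step 3. When do the rules part?** At 12 months if the year runs from first dose. If it runs from week 14, 13 weeks after first dose, they part at 12 + 13 × 7/30.4375 = 15.0 months.

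**Step 4. How many patients could be progression-free then?** Assume exponential PFS, S(t) = 0.5^(t/median), and 60 Phase II patients (section 8.3). The medians are quoted in the protocol for other treatments and populations; applying them here is an assumption.

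| Median PFS, months (source) | S(12) | of 60 | S(15) | of 60 |
|---|---|---|---|---|
| 4.7 (1.1.4, low-dose ipilimumab plus anti-PD-1 after anti-PD-1) | 0.170 | 10.2 | 0.110 | 6.6 |
| 11 (section 1, targeted therapy, low end) | 0.469 | 28.2 | 0.389 | 23.3 |
| 14 (section 1, targeted therapy, high end) | 0.552 | 33.1 | 0.476 | 28.6 |
| 14.9 (1.1.2.2, encorafenib plus binimetinib) | 0.572 | 34.3 | 0.498 | 29.9 |

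For example, 0.5^(12/4.7) = 0.170 and 60 × 0.170 = 10.2. The 24 Phase I patients are subject to the same conflicting text and are not counted.

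**Step 5. What does not depend on duration?** The DLT window closes at the end of week 6 (section 4.7), before maintenance starts. The DLT bounds and the suspension tables in section 8.3 use DLT counts only. Section 8.4 defines the PFS event as progression or death, whatever the treatment status.

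**The case against.** The best defence is that the body of the protocol is consistent. Every body statement of duration carries the cap, and only the Synopsis omits it. A limit worded as up to a year is compatible with earlier stopping for progression or toxicity, and section 3.2 fits a finite course. This makes divergent practice less likely. It does not settle the matter: the Synopsis omits the cap for both regimens, no text joins the two rules, and the start of the year stays open under any reading.

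Three stronger readings are tempting, and the documents do not support them.

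- **That PFS is undefined.** Section 8.4 gives one event definition. Footnote d of the schedules continues imaging every 12 weeks to documented progression, even after a new anticancer therapy starts. Only the treatment whose PFS is summarized is ambiguous, and only in the tail.
- **That every patient progression-free at one year is affected.** Both rules treat alike a patient already off nivolumab for toxicity. Sections 1.1.2.1 and 1.4.2 cite discontinuation for adverse events of 40%, and of 29% within 9 months, for nivolumab plus ipilimumab, though at a different dose ratio. If the year runs from maintenance, the rules part only at about 15 months. Encorafenib, with or without binimetinib, is given continuously, and neither rule mentions stopping it, so the difference concerns one drug.
- **That the 69% one-year PFS cited in section 1.1.4 gives the count, 0.69 × 60 = 41.** It comes from a frontline study not described as high-risk. Section 1.1.3.2 cites a similar 68% for the most favourable prognostic group on another regimen, whereas this trial enrols patients with brain metastases, or elevated LDH with liver or bulky disease.

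**Conclusion.** The contradiction is real and unreconciled. It should be corrected, but its reach is limited. It bears on patients both progression-free and still on nivolumab at about 12 to 15 months, and through them on exposure, late toxicity and the later part of a secondary, descriptive PFS estimate that has no test or power attached.

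For scale, about 10 to 34 of 60 Phase II patients would be progression-free at 12 months and about 7 to 30 at 15 months. These figures rest on the exponential shape and on borrowed medians. They are upper bounds on the number affected under each assumed median, because some of these patients will already have stopped nivolumab for toxicity. Selection of the Phase II regimen on DLTs and the safety monitoring do not change.

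**What to change.** Reconcile the Synopsis (both regimens), the section 4.5 text, the Table 4.5A footnote and footnote a of both Phase I schedules to a single maintenance duration. If a limit applies, state whether it counts from first dose or from first maintenance dose. Make the duration explicit for Phase II, where Table 4.5B is silent, and correct the reference in section 3.5 to a section that does not exist. Which duration applies is for the sponsor's clinical team; this review takes no position on it.

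The cost is a wording amendment, with drug supply following the decision. It is best done before patients reach one year. If any have already passed that point, the report should tabulate nivolumab duration by site beside the PFS estimate.
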